5.3.5. Overall Survival**5.3.5.1. Definition**

Overall survival (OS) is defined as the time from the date of randomization to the date of death.

5.3.5.2. Analysis Methods

Analysis of OS will be based on the ITT analysis set. The Kaplan-Meier method will be used to estimate the distribution of OS for each treatment group. Median OS with 90% CI will be provided. In addition, the number and percentage of subjects who had an OS event or were censored will be reported. The Kaplan-Meier OS curve by treatment group will also be provided.

In addition, the 6-month and 12-month overall survival rate will be estimated by the Kaplan-Meier product-limit method for each treatment group based on the ITT population. The corresponding 90% CI of the 6-month and 12-month overall survival rate will be constructed.

5.4. Other Efficacy Variable(s)**5.4.1. BOD Progression-free Survival****5.4.1.1. Definition**

Biochemical progression is defined as an increase of 25% from nadir value in any one of the following:

- Serum M-component (absolute increase must be ≥ 0.5 g/dL)
- Urine M-component (absolute increase must be ≥ 200 mg/24 hours)
- In subjects without measurable serum and urine M-protein levels: the difference between involved and uninvolved FLC levels (absolute increase must be >10 mg/dL)

Time to biochemical progression is defined as the time from the date of randomization to the date of the first confirmed biochemical progression as defined above.

BOD progression-free survival is the earlier of time to biochemical progression and PFS.

5.4.1.2. Analysis Methods

BOD progression-free survival will be estimated by the Kaplan-Meier product-limit method for each treatment group based on the ITT analysis set. The corresponding 90% CI of BOD progression-free survival will be constructed.

6. SAFETY

Safety assessment will be evaluated through AEs, clinical hematology and chemistry laboratory tests, physical examinations, ECOG performance status, 12-lead electrocardiogram (ECG), and vital signs. Safety analyses will be based on the safety population and presented by the treatment actually received.

6.1. Adverse Events

AEs will be monitored throughout the study. All AEs will be recorded in standard medical terminology and graded according to the National Cancer Institute Common Terminology Criteria for Adverse Events (NCI-CTCAE), Version 4.03. Each occurrence of a given AE will be recorded with the NCI-CTCAE grade. Only the most severe grade over the course of a given episode will be reported. For AE reporting, adverse events will be coded using the latest version of Medical Dictionary for Regulatory Activities (MedDRA) coding dictionary.

All summaries of AEs will be based on treatment-emergent adverse events (TEAEs), defined as any AE that occurs after the first administration of study agent through 30 days after the last study agent administration; or any AE that is considered drug-related (very likely, probably, or possibly related) regardless of the start date of the event; or any AE that is present at baseline but worsens in toxicity grade or is subsequently considered drug-related by the investigator.

The incidence of TEAEs will be summarized overall, by MedDRA system organ class (SOC) and preferred term, by toxicity grade, and by relationship to study agent administration. Specifically, the following AE summaries will be presented:

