### End of Treatment Visits

Unless a subject withdraws consent for study participation or is lost to follow up, an End-of-Treatment Visit is to occur at 28 days  $\pm 7$  days after the last dose of all study treatments. Every effort should be made to conduct the End-of-Treatment Visit before the subject starts subsequent treatment. If a subject is unable to return to the site for the End-of-Treatment Visit, then the subject should be contacted to collect information on AEs and concomitant medications that occur up to 30 days after the last dose of study treatment. Additional information on reporting of AEs is presented in [Section 12](#). Due to the addition of the treatment extension outlined in Amendment 4 which allowed some subjects to resume daratumumab treatment if within 6 months of last dose of Cycle 20, it is possible for subjects to have 2 EOT visits associated with this study. As of Amendment 5, this additional EOT visit associated with treatment extension should be conducted as specified in [Attachment 4](#).

As such, 2 EOT visit CRFs should be completed as applicable for subjects who continued to treatment extension (End of Treatment CRF and End of Treatment Extension CRF).

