### **12.3. Procedures**

#### **12.3.1. All Adverse Events**

All adverse events and special reporting situations, whether serious or non-serious, will be reported from the time a signed and dated ICF is obtained until 30 days after the last dose of study treatment, unless the subject withdraws consent for study participation, or starts subsequent anticancer therapy. For subjects who have received subsequent treatment with therapeutic intent for MM during the adverse event reporting period, only adverse events that are considered to be possibly, probably, or definitely related to daratumumab need to be reported. Serious adverse events, including those spontaneously reported to the investigator within 30 days after the last dose of study treatment, must be reported using the Adverse Event Form. The sponsor will evaluate any safety information that is spontaneously reported by an investigator beyond the time frame specified in the protocol.

Disease progression should not be recorded as an adverse event or serious adverse event term; instead, signs and symptoms of clinical sequelae resulting from disease progression/lack of efficacy will be reported if they fulfill the serious adverse event definition (refer to Section 12.1.1). Death should not be recorded as an adverse event or serious adverse event, but as the outcome of an adverse event. The adverse event that resulted in the death should be reported as a serious adverse event. All events that meet the definition of a serious adverse event will be reported as serious adverse events, regardless of whether they are protocol-specific assessments.

All adverse events, regardless of seriousness, severity, or presumed relationship to study treatment, must be recorded using medical terminology in the source document and the eCRF. Whenever possible, diagnoses should be given when signs and symptoms are due to a common etiology (eg, cough, runny nose, sneezing, sore throat, and head congestion should be reported as "upper respiratory infection"). Investigators must record in the eCRF their opinion concerning the relationship of the adverse event to study therapy. All measures required for adverse event management must be recorded in the source document and reported according to sponsor instructions.

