2.1. Visit Windows

Any analysis that uses time-to-event data will be based on exact determination of time from randomization to the date of the event. For analyses of data by cycle, if data are collected by date (ie, AE onset), the corresponding study evaluations will be assigned to actual sequential cycles, which are derived from the study agent administration data. The start date of a particular cycle is defined as the date of the first scheduled dose, and the end date of a cycle is the start date of the next cycle minus 1. For the last cycle, the end date is defined as the end of treatment visit date or 55 days after the last dose if the end of treatment visit date is not available. If data (eg, laboratory and vital sign, etc) are collected by cycle, the nominal cycle will be used to summarize data.

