6.1.8. Discontinuations Due to Adverse Events

The number and percentage of subjects who discontinued study treatment due to AEs will be summarized by MedDRA SOC and preferred term.

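### A new, unrelated AE that starts 31 to 55 days after an 8-weekly dose and ends treatment falls outside the TEAE tables (SAP 6.1); the gap is wider in Arm B than in Arm A

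*SAP*

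**What the plan says.** SAP 6.1 states: "All summaries of AEs will be based on treatment-emergent adverse events (TEAEs". Its definition has three limbs:

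- By time: "any AE that occurs after the first administration of study agent through 30 days after the last study agent administration".
- By causality, with no time limit: "or any AE that is considered drug-related (very likely, probably, or possibly related) regardless of the start date of the event".
- For pre-existing events: "any AE that is present at baseline but worsens in toxicity grade or is subsequently considered drug-related by the investigator".

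The discontinuation summary in SAP 6.1.8 reads: "The number and percentage of subjects who discontinued study treatment due to AEs will be summarized by MedDRA SOC and preferred term". The overview in SAP 6.1.1 also has a line for AEs that led to stopping.

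Protocol 12.3.1 sets the collection period to match, "until 30 days after the last dose of study treatment". Table 1 and Attachment 4 agree.

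The dosing schedule (SAP 1.2, Protocol 3.1) uses 8-week cycles. Arm A has gaps of 28 days or less through Cycle 7 and one dose per cycle in Cycles 8-20. Arm B has one dose per cycle in Cycles 2-20. Arm C has weekly doses in Cycle 1 only.

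SAP 2.1, which assigns dated events to cycles, ends the last cycle at the end-of-treatment (EOT) visit, "or 55 days after the last dose if the end of treatment visit date is not available". Under Protocol 9.1.3, "an End-of-Treatment Visit is to occur at 28 days" after the last dose, plus or minus 7 days.

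**The concern.** A dose becomes the last dose only in retrospect. On 8-weekly dosing, an AE that starts on day 40 is inside the window if the subject is dosed again on day 56. It is outside if the AE is the reason that no further dose is given. Inclusion therefore depends on whether the event ended treatment, and the events at risk of exclusion are the ones a discontinuation table is meant to show. On-schedule gaps of 28 days or less do not have this problem, so the exclusion differs by arm in a trial that has safety across three schedules as a secondary objective.

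The outputs may also contradict each other. SAP 4.2 reports treatment discontinuations with reasons and has no TEAE restriction. A subject can be counted there as stopped for an AE and be absent from the table in SAP 6.1.8.

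**Working it through.** **Inputs.** Window: 30 days after the last dose (SAP 6.1). Cycle: 8 weeks = 56 days (SAP 1.2). 8-weekly cycles out of 20: Arm A 13 (Cycles 8-20), Arm B 19 (Cycles 2-20), Arm C 0. Arm size: 40. The accrual period and AE rates are not given in the documents.

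**1. The SAP's own figure.** A cycle ends the day before the next one starts: 8 × 7 − 1 = 55 days after the dose, as in SAP 2.1.

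**2. One 8-weekly interval.** Days 0-55 are 56 days. Days 0-30 are covered (31 days) and days 31-55 are not (25 days). 25/56 = 44.6%. An uncovered day is one on which a new, unrelated AE would be excluded if no further dose followed.

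**3. A subject with 52 weeks (364 days) from first dose.** Arm B's 8-weekly doses fall 56, 112, 168, 224, 280 and 336 days after the first dose. Five intervals are complete. The sixth has run 364 − 336 = 28 days, all covered. Uncovered: 5 × 25 = 125; 125/364 = 34%. Arm A is still in Cycles 1-7 (7 × 8 = 56 weeks), with gaps of at most 28 days: 0.

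**4. All 20 cycles (20 × 56 = 1120 days).**

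| Arm | Uncovered days | Share of 1120 days |
|---|---|---|
| A | 13 × 25 = 325 | 29% |
| B | 19 × 25 = 475 | 42% |
| C | 0 | 0% |

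Arm B's share of the combined gap is 475/(325 + 475) = 59%.

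**5. The 12-month cut-off.** Assume uniform accrual, no dropout and doses on schedule. Mean uncovered days per subject:

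| Accrual (months) | Arm A | Arm B | Arm B share |
|---|---|---|---|
| 0 | 0.0 | 125.0 | 100% |
| 6 | 23.3 | 171.2 | 88% |
| 12 | 63.4 | 212.3 | 77% |
| 18 | 103.8 | 253.2 | 71% |
| 24 | 144.2 | 293.8 | 67% |

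At the 6-month cut-off the same accrual range gives 100% down to 73%.

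**6. Likely counts.** Assume that 5% to 15% of 40 subjects stop during 8-weekly dosing for a new, unrelated AE, with onset uniform over the interval. Missing from the TEAE tables: 40 × 0.05 × 25/56 = 0.9, up to 40 × 0.15 × 25/56 = 2.7 per arm.

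**The case against.** The case for leaving the plan alone has several sound parts.

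- **Narrow class of events.** Limbs two and three keep all drug-related AEs and baseline AEs that worsen. Only new-onset events judged unrelated or doubtful, in the final interval, are exposed. This stands.
- **The event need not disappear.** A reader might infer that it leaves every output. It does not: disposition (SAP 4.2), the listing of subjects who discontinued for AEs and the death summaries (SAP 6.2), and the malignancy listing (SAP 6.3.3) are not tied to the 30-day limb. The loss is from the TEAE tables.
- **Non-collection is not established.** Protocol 12.3.1 stops at 30 days, but Protocol 9.5.2 has AEs reported throughout the study, SAP 6.1 opens in similar terms, and Protocol 11.8 includes AEs with onset in the treatment phase without a 30-day limit. A site may well record the event. Exclusion from the tables is firmer than failure to collect.
- **Day 55 is a fallback.** It is tempting to read SAP 2.1 as already treating day 55 as the end of exposure. It applies only when there is no EOT visit date, and it labels cycles; it does not define a safety window.
- **Schedule selection.** A reader might infer that the choice of schedule is biased. Protocol 11.3 and 11.9 base the Phase 3 decision on CR rate and then PD/death rate. Neither makes an AE table a criterion.
- **EOT visit.** A stop decided at the next Day 1, day 56, comes after the visit window of days 21-35. Protocol 10.3 still calls for the visit, so the result is a visit out of window, not necessarily lost laboratory tests or ECG.

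None of this removes the inconsistency in the summary tables.

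**Conclusion.** The point holds as a defect in the TEAE rule. For new, unrelated AEs arising on days 31-55 of an 8-weekly interval, inclusion turns on whether the event ended treatment, and the discontinuation table can disagree with disposition.

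The size is 25 of 56 days per final 8-weekly interval. The difference between arms is real but varies with time. Arm A's zero holds only up to week 56; at the 12-month cut-off Arm B carries between 100% and 67% of the gap under the accrual assumptions above, and over 20 cycles 59%. Multiplying Arm B's time share on 8-weekly dosing (44/52) by 25/56 would suggest 38% at 52 weeks; that ignores the cut-off of the last interval at 28 days, and 34% is the correct count. Nor is cover strictly complete at shorter intervals: the ±5-day cycle window (Protocol 6) and missed doses (Protocol 6.5.2) can stretch a 4-weekly gap past 30 days.

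The expected number of subjects is small, about 1 to 3 per arm of 40 under assumed rates and uniform onset. No sample size, power or alpha depends on it. It deserves correction because the remedy is almost free and the excluded events are those that stopped treatment.

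**What to change.** In SAP 6.1, add a limb: any AE recorded as the reason for stopping study treatment is a TEAE, whatever its onset day. In Protocol 12.3.1, state that such AEs are collected even when they start more than 30 days after the last dose.

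Reconcile the 30-day limit with SAP 2.1 and with Protocol 9.5.2 and 11.8. Reconcile the EOT visit window in Protocol 9.1.3 with stops decided at the next 8-weekly visit.

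If a longer window is also wanted, running to the day before the next planned dose, report it as a supplementary or exposure-adjusted summary. Arm C has no next planned dose and would keep 30 days, so a longer main window in Arms A and B alone would create a new imbalance.

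The cost is a few sentences in each document and slightly higher reported AE percentages in Arms A and B.

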6.1.1. Overview of Adverse Events

An overview of TEAEs will be provided for each treatment group. The overview will include summaries of subjects with any AE, subjects with any toxicity grade 3 or higher AE, subjects with any SAE, AEs leading to study agent dose interrupted, and AEs leading to study agent discontinuation.

6.1.2. Adverse Events by System Organ Class

- Incidence of TEAEs by MedDRA SOC and preferred term
- Incidence of most common (at least 10% in any arm) TEAEs by MedDRA SOC and preferred term
- Incidence of most common (at least 10% in any arm) TEAEs by preferred term

6.1.3. Adverse Events of Toxicity Grade 3 or 4

- Incidence of toxicity grade 3 or 4 TEAEs, by MedDRA SOC, preferred
- Incidence of most common (at least 5% in any arm) toxicity grade 3 or 4 TEAEs, by MedDRA SOC, preferred term

6.1.4. Study Agent-related Adverse Events

- Incidence of TEAEs considered by the investigator to be reasonably related to study agent, by MedDRA SOC and preferred term

6.1.5. Study Agent-Related Grade 3 or 4 Adverse Events

- Incidence of toxicity grade 3 or 4 TEAEs considered by the investigator to be reasonably related to study agent, by MedDRA SOC and preferred term.

6.1.6. Serious Adverse Events (SAEs)

- Incidence of treatment-emergent SAEs, by MedDRA SOC and preferred term

6.1.7. Infusion-Related Reactions

Infusion-related reactions based on investigator assessment will be summarized by treatment group. In addition, subjects with any infusion reactions associated with daratumumab will be listed. The list will include subject ID, treatment group, MedDRA preferred term/verbatim, study day of event, toxicity grade, relationship to study treatment, action taken with study treatment and outcome.

6.1.8. Discontinuations Due to Adverse Events

The number and percentage of subjects who discontinued study treatment due to AEs will be summarized by MedDRA SOC and preferred term.

6.2. Deaths

The number of subjects who died within 30 days of last dose and the number of subjects who died during the study (exclude subjects who died during long-term survival follow-up) will be summarized for all randomized subjects. The primary cause of death collected on CRF page will also be summarized. If the primary cause of death reported is AE, the number of subjects with at least one reasonably related to AE will be further reported.

A list of subjects who died due to AEs during the study (exclude subjects who died during long-term survival follow-up) will be provided.

In addition, subjects with any TEAEs of toxicity grade 3 or higher, SAEs, subjects who discontinued study agent due to AEs will be listed. .

6.3. Adverse Events of Clinical Interest**6.3.1. Infusion-Related Reactions (IRR)**

Subjects with any IRR associated with daratumumab administration will be summarized by MedDRA system-organ class and preferred term. The summaries will be presented by all Grades, and Grade 3 or 4, respectively. In addition, the total number of subjects with IRR in more than 1 infusion will be reported.

6.3.2. Infections and Infestations

Infections and infestations refer to adverse events with MedDRA SOC of infections and infestations. A summary of number of subjects with 1 or more toxicity Grade 3 or 4 treatment-emergent infections and infestations by MedDRA preferred term and relationship to treatment will be provided. In addition, incidences of Grade 3 or 4 treatment-emergent infections and infestation will be summarized by MedDRA preferred term and treatment cycle.

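### The SAP's severe-event tables stop at Grade 4 while its AE overview and listing run to Grade 3 or higher, so a fatal event coded Grade 5 is left out of the severe-AE and severe-infection counts.

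*SAP*

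**What the plan says.** SAP 6.1 has events "graded according to the National Cancer Institute Common Terminology Criteria for Adverse Events (NCI-CTCAE), Version 4.03" and fixes one grade per episode: "Only the most severe grade over the course of a given episode will be reported".

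Four sections then set an upper limit at Grade 4:

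- 6.1.3, severe TEAEs: "Incidence of toxicity grade 3 or 4 TEAEs, by MedDRA SOC, preferred".
- 6.1.5, related severe TEAEs: "Incidence of toxicity grade 3 or 4 TEAEs considered by the investigator to be reasonably related to study agent".
- 6.3.2, infections: "A summary of number of subjects with 1 or more toxicity Grade 3 or 4 treatment-emergent infections and infestations", followed by a second table with the same limit, by preferred term and treatment cycle.
- 6.3.1, infusion-related reactions: "The summaries will be presented by all Grades, and Grade 3 or 4, respectively". Here the limit applies only to the second half of the summary.

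Two outputs have no upper limit. The overview in 6.1.1 counts "subjects with any toxicity grade 3 or higher AE", and the subject listing at the end of 6.2 uses the same cut-off. The SAP gives no reason for having two definitions of a severe event.

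**The concern.** Under a worst-grade rule, an event that passes through Grade 4 and ends in death carries only its final grade. If that grade is 5, a filter that stops at 4 drops the event from the table meant to count severe events. The severe-infection rate in an arm would then be lower because an infection killed the subject than if the subject had recovered from it.

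Infection is where this matters most. Protocol 16.1 names it as a potential risk from the mode of action, and 9.5.2 lists it among the events to be closely monitored. Comparing safety across the three schedules is a secondary objective, and 6.3.2 is the dedicated infection output. It contains no all-grade or Grade 5 table of its own.

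There is also a comparability problem. The protocol's background safety data (1.2.2.3) are given as Grade 3 or higher, so the SAP's severe tables would not be on the same footing.

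**Working it through.** The plan gives no figure to reproduce. The check follows one treatment-emergent event with worst grade 5 through every AE output in SAP 6.1 to 6.3.

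| SAP output | Grade cut-off | Fatal (Grade 5) event |
|---|---|---|
| 6.1.1 overview | 3 or higher | in |
| 6.1.2 all TEAEs by SOC and preferred term | none | in |
| 6.1.3 severe TEAEs | 3 or 4 | out |
| 6.1.4 related TEAEs | none | in, if related |
| 6.1.5 related severe TEAEs | 3 or 4 | out |
| 6.1.6 serious TEAEs | none | in |
| 6.1.7 infusion-reaction summary and listing | none | in, if such a reaction |
| 6.2 listing | 3 or higher | in |
| 6.2 death summary and list of AE deaths | not by grade | in, if within the section's window |
| 6.3.1 infusion reactions, all-grade part | none | in, if such a reaction |
| 6.3.1 infusion reactions, severe part | 3 or 4 | out |
| 6.3.2 infections by preferred term and relationship | 3 or 4 | out |
| 6.3.2 infections by preferred term and cycle | 3 or 4 | out |

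The 6.1.6 row relies on protocol 12.3.1, which requires the event that led to death to be reported as serious.

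**Size.** In one arm, let N be the treated subjects, s those with at least one infection of Grade 3 or higher, and f those among the s whose only such infections ended at Grade 5. A subject with a separate Grade 3 or 4 infection still appears, so is not in f.

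- Count shown in 6.3.2: s − f. Count on the overview's definition: s.
- Shortfall in the rate: f/N.
- Relative shortfall: f/s.

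The documents give neither s nor f. Taking N = 40, the planned arm size, and assuming that all are treated:

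- f = 0: no shortfall.
- f = 1: 1/40 = 2.5 percentage points.
- f = 2: 2/40 = 5.0 percentage points.

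The relative shortfall f/s runs from 0, when no infection is fatal, to 1, when every subject with severe infection is in f and the table shows zero.

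**Knock-on effect in 6.1.3.** Its second table keeps terms reaching 5% in any arm. With N = 40 that is 0.05 × 40 = 2 subjects. A term with two severe cases in an arm, one of them fatal, would count as 1/40 = 2.5% there and would drop out of the table unless another arm reached the threshold.

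**The case against.** The strongest reply is that nothing fatal goes unreported. This largely stands. A reader might infer that a fatal infection or reaction vanishes from the safety report; the documents do not support that. A fatal infection appears by system organ class and preferred term in 6.1.2, in 6.1.4 if related, and in 6.1.6, and it enters the 6.2 listing and, within its window, the death outputs. A reader might also infer that the infusion-reaction tables are confined to Grades 3 and 4. They are not: 6.3.1 also gives all grades, and 6.1.7 lists each reaction with its grade and outcome. What no other output supplies is infection by treatment cycle, and none of them corrects the severe count itself.

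Second, Grade 5 coding is an assumption. Protocol 12.1.3 and SAP 6.1 cite NCI-CTCAE without defining the grades, and protocol 12.3.1 records death as the outcome of an event. A site that left a fatal event at Grade 4 would keep it in the tables. This stands as a caveat. But a cut-off of Grade 3 or higher differs from Grade 3 or 4 only if a grade above 4 is in use, and possible variation between sites is itself a reason to state the rule.

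Third, SAP 6.1 promises TEAE incidence "by toxicity grade, and by relationship to study agent administration", which might cover Grade 5. The specific summaries that the section then lists contain no full breakdown by grade, so this cannot be relied on.

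Fourth, different outputs may legitimately use different cut-offs. That is fair: no two passages give conflicting rules for the same table, so this is an unexplained inconsistency and not a strict contradiction.

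Finally, fatal events may be rare. Protocol 1.2.2.3 reports no deaths from daratumumab-related AEs, with approximately 300 subjects treated at that cutoff (1.2.2). That figure covers related events only, whereas 6.1.3 and 6.3.2 count events regardless of cause.

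**Conclusion.** The point holds in a limited form. Read literally, and assuming that fatal events are graded 5, the tables in 6.1.3, 6.1.5 and 6.3.2 and the severe part of 6.3.1 exclude the worst outcome. Their counts can be too low and need not agree with the 6.1.1 overview. The size depends on the number of fatal TEAEs: nil if there are none, and 2.5 percentage points per affected subject in an arm with 40 treated. The documents support no particular percentage understatement beyond that.

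This is a matter of definition and presentation in descriptive safety reporting. No planned test, stopping rule or decision rests on these tables, and the efficacy analyses are untouched. It is still worth correcting, because infection is a named risk and the SAP already uses the wider cut-off elsewhere.

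**What to change.** In SAP 6.1.3, 6.1.5, both tables in 6.3.2 and the severe part of 6.3.1, replace Grade 3 or 4 with Grade 3 or higher, and show Grade 5 in its own column. Change the titles of 6.1.3 and 6.1.5 to match. Add one sentence to 6.1: *An adverse event with a fatal outcome is counted as Grade 5.* As a programming check, the number of subjects in the total row of 6.1.3 should then equal the Grade 3 or higher line of the 6.1.1 overview.

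The cost is a wording change and one extra column per table, with no new data. Severe-event percentages may rise slightly; the Grade 3 and 4 counts remain visible in their own columns for anyone who needs them.
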